***The goal of this Phase I study is to determine whether intravenous infusion of ALLO attenuates (1) stress-induced alcohol craving, stress-induced anxiety and (2) subjective stimulant/sedative effects of alcohol in individuals with AUD using a laboratory paradigm.*** The secondary objective of this project is to characterize the behavioral effects of ALLO in AUD. We propose a double-blind, randomized, between subject, placebo-controlled study in 60 individuals with AUD to compare *one dose (1.5 mg/ml solution) of continuous (200 min.) infusion of ALLO* (targeted plasma of 100 nM [IV bolus of 191 mcg/kg over 60 min. followed by continuous infusion of 57.4 mcg/kg/hr x 140 min.] n=30) to *placebo* (n=30). On a single test day, after 60 min of infusion - when ALLO levels stabilize - stress and neutral cues consisting of personalized 5 min. scripts will be presented in random order. The use of personalized scripts has been shown to produce robust and reliable craving and anxiety in subjects including heavy drinkers[1], alcohol dependent individuals (see the preliminary data section)[2] both with and without psychiatric comorbidity (including work by our group)[3-5] and, in those with other substance use disorders [6]. All participants will also receive alcohol administered intravenously using a clamp procedure, targeting a breath alcohol concentration (BrAc) of 40mg% (40 mg/dL). Alcohol will be administered following script presentation (20 min to target and clamped for

additional 30min). The main outcomes are measures of stress-induced alcohol craving, stress-induced anxiety, and subjective alcohol effects; other secondary outcomes include subjective mood effects, cognitive performance, and motor coordination.

**Hypothesis 1 (Specific Aim 1):** To determine if ALLO (targeted plasma of 100 nM), compared to placebo:

**Aim #1a:** attenuates stress-induced craving for alcohol, measured by the Alcohol Urge Questionnaire (AUQ).

**Aim #1b:** attenuates stress-induced anxiety, measured by the State Trait Anxiety Inventory (STAI-6).

**Aim #1c:** attenuates the subjective stimulant/sedative alcohol effects (target BrAC=40 mg%), measured by the Biphasic Alcohol Effects Scale (BAES).

**Hypothesis 2 (Specific Aim 2):** To characterize ALLO's behavioral effects:

**Aim #2:** to describe ALLO's subjective mood effects, we will use Differential Emotions Scale (DES-R), the Addiction Research Center Inventory (ARCI) and the Similarity to Drugs of Abuse Scale (SDAS).

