**Neurosteroids in alcohol drinking behavior and AUD:** A substantial body of preclinical and human studies show that neuroactive steroids have a role in alcohol reinforcement, tolerance, dependence and withdrawal. Data also indicates that neurosteroids, and ALLO in particular, may have significant therapeutic potential in AUD because of their ability to normalize a dysregulated HPA axis response typically found in chronic alcohol abuse. **A2a.** *In preclinical studies:* Alcohol increases the levels of progesterone (PROG) and ALLO in alcohol-preferring and non-preferring rats [13-15]. Administration of ALLO increases alcohol self-administration in non-dependent rats and in non-dependent alcohol-preferring rats. However, chronic ethanol consumption in rats leads to decreases in plasma neurosteroid release [16-18], and decreased levels of ALLO after reintroduction of alcohol in alcohol-withdrawn animals[19]. Similarly, female monkeys who drink excessively tend to experience disruptions in their menstrual cycle, putatively due to neurosteroid depletion and low levels of ALLO [20]. *Rodents who consume high doses of alcohol for long periods of time show decreases in alcohol consumption after a single infusion of ALLO [19, 21] suggesting ALLO may play an important compensatory role in mediating alcohol effects.* **A2b.** *In healthy humans:* Similar to preclinical studies in healthy humans: a) alcohol intoxication increases plasma levels of ALLO [22, 23], b) ALLO levels are correlated with levels of intoxication [22, 23] and subjective effects (“liking” or “wanting” more alcohol)[24], c) pretreatment with finasteride (reduces the formation of ALLO and PROG) blocks subjective stimulant effects of alcohol[24] and reduces drinking in men[25], and a single dose of dutasteride attenuates subjective sedative effects in non AUD men [26], d) women are less sensitive to the effects of alcohol and drink more during the follicular phase of their cycle, when ALLO levels are at their lowest [27]. There are some negative studies that show no relationship between intoxication and ALLO levels at lower doses of alcohol [28], in women in the follicular phase[29] or the luteal phase [30], and find lower levels of PROG and ALLO after alcohol administration [31]. **A2c:** *In humans with AUD:* Mirroring preclinical studies, women who drink excessively tend to experience disruptions in their menstrual cycle presumably due to neurosteroid depletion and lower levels of ALLO[32]. Dysregulation in HPA axis function has been reported in individuals with AUD while they are actively drinking, during withdrawal, and during abstinence [33-35]. Also, suppression of neurosteroid release has been reported in individuals with AUD as well as their relatives after administration of naloxone [35, 36]. A recently published study examined the effect of progesterone stimulated ALLO in cocaine dependent men and women on stress-induced craving, mood, and cognitive functioning. High levels of ALLO were associated with decreased craving, increased mood ratings, and improved cognitive performance suggesting ALLO may have important therapeutic utility in addiction. *In conclusion, data from animals and humans show that ALLO may have a significant therapeutic potential although there are no studies to date that examine the role of ALLO administration in AUD.*

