drop (in about 20-40 min.). The approach of delivering the dose continuously with an infusion pump over the 200 min period will still result in fluctuating plasma levels but the fluctuations will not be as precipitous as those using bolus infusion. **2.** The high cost of ALLO (\$4175 per subject) combined with limited funding restricted our design to a single dose of ALLO, although a dose-ranging strategy would have generated important results regarding ALLO's dose-ranging efficacy. **3.** Personalized scripts were selected for stress induction rather than other stressors (Trier Social Stress test, or Cold Pressor Test) because they most reliably invoke stress in the lab [63], and they have been used to induce drug and alcohol craving. **4.** We decided to administer both scripts in one laboratory session based on the review of the evidence from laboratory studies in addition to practical considerations. The proposed design has been successfully used by our group and others in numerous imaging studies with healthy subjects and individuals with Axis I disorders. The current design will also limit subject drop outs by significantly reducing the number of lab sessions. **5.** Because the same stress condition cannot be administered on more than one occasion, a within subject design is not feasible for this study.

**Justification for inclusion/exclusion criteria:** **1.** We plan to enroll both men and women since ALLO has been safely given to both genders. We believe that gender limitations will make recruitment very difficult, and including both genders will make the study more generalizable. Also, since there are some indications that healthy men may be more sensitive to the effects of ALLO infusion than healthy women, it seems imperative to further elucidate possible gender differences by including both genders in the study design. **2.** We are including smokers because of very high rates of smoking among heavy drinkers. In order to control for possible withdrawal during the lab session, all smokers will be allowed to have a cigarette before the beginning of the laboratory session.

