**Cognitive functioning:** Little is known about the effects of ALLO on cognitive functioning. However, GABA receptor agonists have been studied extensively and are known to negatively affect cognition. The effects of ALLO on various aspects of memory have been studied in animals and the data show that ALLO impairs spatial, working, and long-term memory [66, 67]. Only one study examined the effects of ALLO administration in healthy women and found that 0.07 mg/kg of ALLO had a statistically significant but relatively minor effect on verbal memory but no effect on semantic or working memory [37]. Verbal memory will be evaluated using *The Hopkins Verbal Learning Test-Revised (HVLT-R)*. The HVLT-R is a word list learning test of verbal memory. The main outcomes for the HVLT-R are percent corrected for immediate and delayed recalls. GABAa agonists have also been shown to affect response inhibition or the ability to suppress a response in rare and irregular situations[68, 69]. We will use the **Go No-Go task** to evaluate response inhibition [70]. A series of rectangles are presented every 1150 ms and participants are instructed to press a spacebar when they see a green rectangle (=go) but refrain from pressing the spacebar when they see a blue rectangle (=no go), and to give equal importance to speed and accuracy. The primary outcome is the number of commission errors. **Motor Coordination:** The negative effects of GABAa agonists on motor coordination have been well documented and studied for decades[71]. Motor coordination will be assessed using the **Grooved Pegboard Test** (Lafayette Instrument Company). This test is a manipulative dexterity test, consisting of a board with randomly positioned slots in which subjects insert pegs. It is an eye-to-hand coordination test that has been used in research studies, including pharmacotherapy studies [72].

**Plasma ALLO:** Deidentified plasma levels of ALLO will be analyzed by [name] lab at UCDavis. Plasma samples will be obtained on multiple time points during the lab session (see Table in Human Subjects section) to examine how levels of ALLO relate to: a) mood, cognitive performance and motor coordination, and b) stress-induced craving and anxiety.

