## 6. PROTECTION OF HUMAN SUBJECTS:

Human subjects: Non-treatment seeking individuals with AUD will be recruited from the New Haven area by newspaper advertisements, Craigslist, and flyers. Based on previous human laboratory studies, approximately 10 percent of the subjects who enroll in the study, meet all inclusion/exclusion criteria and are randomized are expected to either drop out or be terminated because of non-compliance with the study procedures. To meet the target sample of 60 completers, a total of 66 participants will be randomized. After the initial phone screening, potential subjects will undergo a comprehensive evaluation that is summarized in Table 1 in “Research Strategy”.

Study Procedures: Table 1 delineates the timeline for study procedures and measures that will be administered at each time point during the laboratory session.

Table 2. Study Procedures (times are approximate)

Time	Measures and Events
Baseline	Urine and BAC check, HR/BP, CIWA, TLFB, AUQ, STAI-6, VAS; BAES, NDS, DES-R, ARCI, SDAS, HVLT-R, Go no-Go, Grooved Pegboard Test, Ghrelin, NPY and ALLO levels, breakfast
-62 min	Ghrelin and NPY levels
-60 min	ALLO infusion starts
-40 min	HR/BP, AUQ, STAI-6, VAS; BAES, NDS, DES-R, ARCI, SDAS, HVLT-R, Go no-Go, Grooved Pegboard Test, ALLO levels
-20 min	HR/BP, ALLO levels
-2 min	Ghrelin and NPY levels
Stress Reactivity Condition 1 (15 min break)	
0 min	Condition 1. (Neutral or Stress) Baseline/Relaxation; BP & HR, AUQ, STAI-6, VAS
+10 min	Image period, BP & HR
+15 min	BP&HR, AUQ, STAI-6, VAS, Ghrelin and NPY levels
+20 min	Recovery period. AUQ, STAI-6, VAS
+25 min	BP&HR, AUQ, STAI-6, VAS, Ghrelin, NPY and ALLO levels

Stress Reactivity Condition 2	
+30 min	Condition 2. (Neutral or Stress). Baseline/Relaxation as described above
+40 min	Image Period as described above
+45 min	BP&HR, AUQ, STAI-6, VAS, Ghrelin and NPY levels
+50 min	Recovery Period as described above
+55 min	BP&HR, AUQ, STAI-6, VAS, BAES, NDS, DES-R, ARCI, SDAS, Ghrelin, NPY, and ALLO levels
Alcohol Infusion	
+70 min	start of IV alcohol infusion
+90 min	Target reached STAI-6, VAS, BAES, NDS, ARCI, SDAS, HVLT-R, Go no-Go, Grooved Pegboard
+118 min	Ghrelin and NPY draw
+120 min	IV alcohol infusion ends, ALLO infusion ends
+150 min	STAI-6, VAS, BAES, NDS, ARCI, SDAS, HVLT-R, Go no-Go, Grooved Pegboard, ALLO levels, Lunch

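### Plasma ALLO is not measured while alcohol is running or at the end of the 60-min load, although blood is already drawn at both times

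*Combined protocol and SAP*

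**What the plan says.** Section 2 (Purpose) gives the infusion as "IV bolus of 191 mcg/kg over 60 min. followed by continuous infusion of 57.4 mcg/kg/hr x 140 min", 200 min in all, and places the cues "after 60 min of infusion - when ALLO levels stabilize". Aim 1c in that section is the effect of ALLO, at a targeted 100 nM, on BAES stimulant and sedative scores under alcohol.

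Section 5, under Plasma ALLO, states that "Plasma samples will be obtained on multiple time points during the lab session" and points to the table in the human-subjects section for the times. Levels are to be related to mood, cognition and motor performance, and to craving and anxiety under stress.

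Table 2 in section 6, whose times are stated to be approximate, has these rows:
- -60: "ALLO infusion starts".
- -40: full battery with an ALLO level.
- -20: "HR/BP, ALLO levels".
- -2: ghrelin and NPY only.
- +25 and +55: ALLO levels with ghrelin and NPY.
- +70: alcohol starts.
- +90: BAES, several mood scales, cognitive and motor tests; no blood sample.
- +118: "Ghrelin and NPY draw".
- +120: both infusions end.
- +150: battery repeated, with an ALLO level.

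No other section adds an ALLO sample.

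**The concern.** The only BAES ratings and cognitive and motor tests made while alcohol is running are at +90. The nearest ALLO levels are 35 min earlier, before any alcohol, and 60 min later, after both infusions have ended in Table 2.

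This matters because the protocol itself gives reasons not to assume a constant level. It expects plasma levels to fluctuate under continuous infusion. It describes the study as the first to combine the two agents. Its background section reports that in healthy people "alcohol intoxication increases plasma levels of ALLO", while also citing studies with no relationship and one with lower levels.

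If Aim 1c is null, a reader will ask whether ALLO was near 100 nM during the clamp, and no level was taken then to answer that. The planned level-response work on mood, cognition and motor performance has no level under alcohol to pair with the +90 results.

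A lesser gap is that cue testing assumes a stable level at 60 min, but the last level before the first cue is taken 40 min into the 60-min load.

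**Working it through.** **1. Infusion length.** Section 2: 60 + 140 = 200 min, which from -60 ends at +140. Table 2: -60 to +120 = 180 min. The +150 sample is therefore 30 min or 10 min after the stop, depending on which passage is followed.

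**2. Count of samples.**
- Alcohol window, +70 to +120: ALLO 0, ghrelin/NPY 1 (+118).
- Alternative 30-min ascent plus 30-min clamp, +70 to +130: ALLO 0, ghrelin/NPY 1 (+118).
- Last 15 min of the load: ALLO 0, ghrelin/NPY 1 (-2).
- Distance from the +90 battery: 90 - 55 = 35 min back; 150 - 90 = 60 min forward.

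These counts need no assumption.

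**3. How far could the +90 level differ from +55 without any alcohol effect?** The documents give no half-life, so I assume one compartment and vary the half-life. With R1 = 191 and R2 = 57.4 mcg/kg/h, k = ln 2 / half-life in hours, and the maintenance steady state scaled to 100:
- load, h hours from start: C = 100 × (R1/R2) × (1 - e^(-kh));
- maintenance: C = 100 + (C at 1 h - 100) × e^(-k(h-1));
- after the stop: multiply by e^(-k × time since stop).

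| Half-life (h) | +55 | +90 | +118 | +150 (stop at +120) | +90/+55 | +150/+90 |
|---|---|---|---|---|---|---|
| 0.33 | 128.0 | 108.2 | 103.1 | 36.0 | 0.845 | 0.333 |
| 0.5 | 142.0 | 118.7 | 109.8 | 54.7 | 0.836 | 0.461 |
| 1 | 135.2 | 123.5 | 117.0 | 82.4 | 0.913 | 0.668 |
| 1.94 | 100.0 | 100.0 | 100.0 | 83.6 | 1.000 | 0.836 |
| 6 | 42.7 | 46.4 | 49.2 | 46.7 | 1.087 | 1.005 |

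So +90 is 0.84 to 1.09 times +55, whereas +150 is anywhere from 0.33 to 1.01 times +90.

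**4. Half-life implied by the stated rates.** The level is flat after the load only if 1 - e^(-k) = 57.4/191 = 0.3005. Then k = 0.357 per hour and the half-life is 0.693/0.357 = 1.94 h. At that value the +150 level, as a share of the end-of-infusion level, is 0.5^(0.5/1.94) = 0.84 for a stop at +120 and 0.5^(0.167/1.94) = 0.94 for a stop at +140.

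**5. End of load.** In the same model the -2 level is 1.15 (0.33 h) to 1.43 (6 h) times the -20 level, so -20 does not stand in for the end of the load.

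**6. What a +118 level would add.** Interpolating to +90 gives weight 35/63 = 0.556 to +118 and 0.444 to +55. At 0.33 h this is 0.444 × 128.0 + 0.556 × 103.1 = 114.2, against a modelled 108.2 (about 6% high). At 6 h it is 46.3 against 46.4. Using +55 alone is 142.0/118.7 = 1.20, or 20% high, at 0.5 h. An alcohol effect beginning at +70 would also show in +118, and it cannot show in +55.

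**The case against.** The other side has a good case on several points.

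- **Exposure is not a blank.** The +55 sample is taken on the same maintenance infusion, and step 3 shows that it bounds +90 usefully. This stands. The gap is that exposure under alcohol is not measured, not that nothing is known about it.
- **No planned primary analysis uses a level.** Medication enters the mixed model as a two-level category, so Aim 1c is a comparison of randomised groups. A reader might infer that the missing level biases it; it does not.
- **The evidence on alcohol and ALLO is mixed.** The background section also cites null findings at lower alcohol doses and in follicular-phase women, when women are tested here. It gives endogenous ALLO below 1 nmol/L in that phase, comparable in men. A fivefold rise from 1 nmol/L would add 4 nM to a 100 nM target, or 4%. This stands for endogenous ALLO. An effect of alcohol on clearance of infused ALLO is a separate possibility, which the documents neither claim nor exclude.
- **Many planned pairings exist.** The -40, +55 and +150 assessments each have a concurrent level, and the Plasma ALLO paragraph does not list subjective alcohol effects. This stands in part: section 5D does examine mood, cognition and motor performance in combination with alcohol, and +90 is when these are tested with alcohol running.
- **The remedy is partial.** The +118 draw is 28 min after +90, and -20 and +25 already bracket the first cue. Both are true, so the -2 assay is the less valuable addition.

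A reader might also take the protocol's description of the fall after a rapid push, "drop (in about 20-40 min", as a half-life and conclude that +150 understates exposure by 16% to 65%. The documents do not support that. The phrase describes how soon levels fall after a bolus, and the protocol contrasts the infusion with a bolus on exactly this point. Half-lives of 20 and 40 min would also clash with the stated rates: the level would settle at 0.3005/(1 - 0.125) = 34% and 0.3005/(1 - 0.354) = 46% of its end-of-load value.

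**Conclusion.** The concern holds as a limit on interpretation. None of the six scheduled ALLO levels falls while alcohol is running under either ascent method, and none falls in the last 15 min of the load, though blood is drawn at both times. This rests on Table 2 alone.

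The consequence is modest. Without an alcohol effect, the +90 level is 0.84 to 1.09 times the +55 level, assuming one compartment and half-lives of 0.33 to 6 h. That bound cannot cover a change in ALLO caused by alcohol, which is the open question in a first combined study. A null Aim 1c would be harder to interpret, and the +90 battery has no level taken under alcohol for the level-response analyses. No power or sample-size figure changes.

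This is a worthwhile, inexpensive improvement rather than a flaw in the primary analysis.

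**What to change.** 1. In Table 2, add an ALLO level to the existing -2 and +118 draws. ALLO samples rise from 6 to 8, and both gaps go from 0 to 1 with no new draw time.
2. State in section 5 that the exposure value for the +90 outcomes combines +55 and +118, for example interpolated to +90, and that +150 outcomes are paired with the +150 level.
3. Use the -2 level to check that the 100 nM target is reached before the first cue.
4. Reconcile the 180-min infusion in Table 2 with the 200 min stated elsewhere, so that the time from stop to the +150 sample is defined.

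**Cost:** 2 × 60 = 120 more assays for 60 completers, and a small addition to the stated 140 ml of blood (aliquot size is not given). The +118 level is still not simultaneous with +90; a sample at +90 itself would need a new draw.

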## 6.1 Risk to the subjects

Human subject's involvement and characteristics:

Sources of material: The subject will be the source of material. They will be informed that the research material collected will be for research purposes only. Blood, plasma, and urine samples will be obtained from study participants. The blood samples will be obtained with standard venipuncture techniques. In addition, physiological (heart rate and blood pressure), cognitive performance, and subjective measures will be obtained.

Potential risks: There are potential risks, discomforts and inconveniences associated with the participation in this study. These may be due to allopregnanolone (ALLO) administration, IV alcohol administration, combination of ALLO and alcohol, stress induction, blood draw and loss of privacy.

- 1) Allopregnanolone: In this study we will use a targeted plasma of 100 nM of ALLO. This dose of ALLO is similar to the levels found in women in their third trimester of pregnancy. Similar doses have been safely given to healthy participants with minimal and transient side effects. Common adverse effects associated with single administration of ALLO are sedation, alcohol-like intoxication, headaches, mild nausea and flushing. Less common side effects associated with neurosteroids, such as progesterone, and reported after long-term use include depression, anxiety, blockage of blood vessels, and increased risk for heart attack or stroke.
- 2) IV alcohol administration: Adverse effects resulting from ethanol consumption include blurred vision, nausea, vomiting, flushing, headache, and lightheadedness. These side effects should reach their peak within 1.5 hours following consumption of alcohol and decline thereafter.
- 3) Combined administration of ALLO and alcohol: We anticipate that ALLO will attenuate the sedative and stimulant effects of alcohol. However, since this will be the first instance the two compounds are given together all participants will be continuously monitored, a physician and/or a nurse will be present during the laboratory session at all times.
- 4) Stress induction: The interview, questionnaires, and imagery sessions will require subjects to discuss stressful experiences. These procedures are expected to cause a moderate degree of anxiety, psychological discomfort, and alcohol craving that will return to baseline levels before the subjects are sent home. If the subject continues to experience unpleasant symptoms a few hours after the end of the procedures, clinically-trained staff will guide the subject through relaxation techniques. If urges to drink or emotional distress persist after an hour of relaxation training, the subject will receive an individual counseling session with a psychologist who is

experienced in psychotherapy. If urges to drink or emotional distress persist after the psychotherapy session, the subject will be escorted to the Emergency Department and treated by the on-call psychiatrist.

- 5) Blood Drawing: Subjects will have approximately 140 ml of blood drawn as a result of their participation in the study. Blood drawing can cause some pain and may result in bruising.
- 6) Loss of confidentiality: Participation in the study may lead to loss of confidentiality.

